5.4.3 Supportive nonclinical experience with fenretinide

5.4.3.1 Mechanism of Action in Cancer and other Indications

Fenretinide appears to act by different pathways than those mediated by retinoid receptors. Studies in breast cancer cell lines have demonstrated that fenretinide has a low binding affinity for nuclear retinoic acid receptors (RARs) compared with trans-retinoic acid. Despite the similarities with other retinoids, comparative studies with the parent compound ATRA (all-trans-retinoic acid) suggest that fenretinide mediates its key apoptotic and anti-tumor cytotoxic activity through a novel mechanism, not completely understood^{48, 49, 50, 51}, potentially involving modulation of saturated and unsaturated ceramides in cell lines from various tumors. Furthermore, evidence shows that another of the drug's molecular targets is mammalian Target Of Rapamycin "mTOR", which is a central control of cell growth and division. The differential responsiveness of numerous cell lines, confirms that fenretinide has a mechanism of action distinct from the retinoid receptor pathway.

Fenretinide was also shown to form complexes with the retinol binding protein (RBP)4, reducing serum concentrations of retinol (vitamin A), which is potentially associated with the reversible delayed dark adaptation (nyctalopia, also called night blindness) in some patients. However, the effect on RBP4 is also a potential disease-modifier in dry age-related macular degeneration (AMD), an unaddressed chronic eye disease that causes vision loss in the center of the field of vision. Reducing the delivery of RBP4-retinol to the retinal pigment epithelium (RPE) was postulated to reduce the accumulation of the toxic metabolite retinylidene-N-retinylethanolamine "A2E" thus slowing geographic atrophy (GA) lesion growth. A two-year

Phase IIb proof-of-concept trial with FRD in dry AMD reported a trend for reduced GA lesion growth rates in patients who achieved serum levels of $\leq 1 \mu\text{M}$ ⁵².

Other groups showed that fenretinide inhibits obesity and insulin resistance in mice and is in early clinical trials for treatment of insulin resistance in obese humans. In another study, long-term fenretinide treatment prevents high-fat diet-induced obesity, insulin resistance, and hepatic steatosis. The mechanisms of action involved are the RBP and the PPAR γ ⁴⁴.

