7.1.4 Exploratory Endpoints

- The change from pre-study in AA, DHA and EPA in phospholipids and metabolipidomic markers (eicosanoids and docosanoids), LAU-7b compared to placebo;
- The change from pre-study in plasma oxidative stress makers (malondialdehyde, nitrotyrosine), LAU-7b compared to placebo;
- The changes from pre-study of in plasma ceramide subclass concentrations, LAU-7b compared to placebo;
- The change in plasma lipidomics (AA, DHA, AA/DHA ratio and EPA), inflammation markers, plasma oxidative stress markers, FEV₁, body weight and BMI measurements, between the start and the end of IV-treated PEx (performed only in patients who receive IV antibiotics for what their treating physician considers an exacerbation), LAU-7b compared to placebo;
- The change from pre-study in systemic bone formation/resorption markers, LAU-7b compared to placebo;
- At specific clinical sites, the change in bone density from baseline through 24 weeks of treatment, LAU-7b compared to placebo;
- At specific clinical sites, the changes in clinical scoring using the Matouk Disease Score contrasting the post-treatment score to the pre-study score, LAU-7b compared to placebo;
- Correlation of plasma retinol and retinol-binding protein levels measured during the study with ophthalmological assessments.

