11.5 Ophthalmologic Examinations and Night Vision Questionnaire

A particular attention will be paid to ophthalmological safety, since fenretinide is known to cause a decrease in circulating vitamin A that may result in symptoms of nyctalopia, generally mild and rapidly reversible. In order to capture as much information as possible on ophthalmological TEAEs, ophthalmological assessments are performed at planned timepoints, and include both specific tests and use of a patient questionnaire. At screening, a Night Vision Questionnaire (NVQ) will be self-administrated, along with a full ophthalmological examination, and any abnormality will be recorded in the e-CRF. Clinically significant abnormalities may result in exclusion from the study, in particular low light vision abnormalities or dark adaptation abnormalities.

Moreover, the NVQ will be used according to the Schedule of Events, Section 2, to ask three (3) specific questions probing possible ophthalmological AEs. These questions will cover the following elements: Question 1: Dark adaptation difficulties; Question 2: Vision in condition of poor luminosity; Question 3: Recovery after dazzling. Results will be compared to previous occurrence to detect changes. Furthermore, possible ophthalmological AEs will be sought using non-suggestive questions at intermediate assessments done via phone calls. Details and specific questionnaire sheets are presented in the Study Reference Manual.

Proposed escalating safety monitoring of dark adaptation in planned Phase 2

Step 1: Night Vision Questionnaire (NVQ)

A specific questionnaire will be employed to assess the extent of reported symptoms and to trigger an escalation of objective assessments to determine if indeed the reported symptoms translate into a confirmed episode of nyctalopia. Also, a severity grading using CTCAE shall be used in order to qualify the confirmed episode of nyctalopia. The planned NVQ is presented below:

Question 1. Dark adaptation difficulties: In comparison with people around you, do you adapt easily to semi-obscurity when going from a bright to a dim environment, such as daylight to a movie theatre or tunnel.

Question 2. Vision in condition of poor luminosity: Are you able to perceive the outlines of objects in a domestic and semi-obscure environment, such in the indoor candlelight or poor streetlight, or to see the content of closets and kitchen cabinets?

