Question 3. Recovery after dazzling: When you transition from a semi-obscure environment to a strongly lit one, do you remain dazzled?

Questions Q1 and Q2: Y (Yes) means normal. Questions Q3: N (No) means normal.

Assessment of the extent of reported symptoms: Level 0: no abnormal answer; Level 1: one abnormal answer; Level 2: two abnormal answers; and Level 3: three abnormal answers.

NVQ administration: Screening, Day 21, Day 77, Day 161, Day 189.

Level 1 NVQ will result in the given symptom to be considered a Grade 1 AE. However, it will not trigger an escalation to Step 2. Level 2 or 3 NVQ will automatically trigger a complete ophthalmological examination (Step 2) and its AE severity graded by the ophthalmologist.

Step 2: Complete ophthalmological examination, including specific dark adaptation tests

Administration: Screening, Day 77 and Day 189, and following any Level 2-3 NVQ report.

Suggested dark adaptation test to be included: a test able to evaluate dark-adaptation changes such as cone-rod break and the final rod threshold (see note below). Severity grading using CTCAE to be performed on confirmed nyctalopia episodes. If the reported symptoms do not get confirmed by the objective measures in Step 2, the default CTCAE severity Grade 1 will be used.

Step 3: Electroretinogram (ERG)

Administration: to be performed only if clinically indicated, in particular if the ophthalmological examination results are equivocal, or the type of signs/symptoms requires it.

Ophthalmologic examinations will be performed by (or under the oversight of) a licensed ophthalmologist at screening, Day 77 and Day 189 visits. It can also be triggered on demand if a patient reports signs of ophthalmologic nature upon questioning or at the time of the scheduled ophthalmologic questions posed on several occasions, according to the Schedule of Events, page 10.

The scheduled complete ophthalmologic examination will consist of the following: Examination of visual acuity, examination for amblyopia, examination of eyelids, conjunctiva, cornea, pupillary reactions to light and accommodation, low contrast visual function (Contrast Sensitivity), specific dark adaptation testsⁱⁱⁱ, lens,

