12.5 Safety Analyses

The safety analyses will be performed at least thrice, 1- when a minimum of half of the enrolled patients have completed at least one dosing cycle and corresponding safety information is available, along with Day 21 plasma retinol and retinol binding protein concentration data, 2- when at least half of the enrolled patients have completed a minimum of 3 dosing cycles and corresponding safety information is available, along with Day 77 plasma retinol and retinol binding protein concentration data, and 3- at the time of final analysis. Safety analyses will be performed on the safety population (those patients who receive at least one dose of study drug). Blinded safety data will be assessed by the DSMB at regular meetings. The DSMB may request unblinding of patients for safety concerns in addition to receiving the unblinded mid-study analysis results. The study will remain double blinded to the Investigators, patients and sponsor's staff until the end of the study, unless circumstances require unblinding.

Safety and tolerability will be assessed by the following:

- Adverse events described and categorized according to the MedDRA, version 16 or more recent.
- Clinically relevant changes from baseline in vital signs
- Clinically relevant changes from baseline in 12-lead ECG
- Clinically relevant changes from baseline in physical examinations
- Clinically relevant changes from baseline in safety laboratory assessments (hematology with differential count, biochemistry, and urinalysis)

- Plasma retinol and retinol-binding protein values, changes from screening/baseline, correlated with ophthalmological symptoms, more specifically nyctalopia
- Change in PEx incidence and antibiotic treatment requirement.

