- TEAEs leading to treatment discontinuation;
- Serious TEAEs;
- Fatal TEAEs.

All safety analyses will be performed on the Safety population.

Additional Safety Evaluations

The following safety evaluations, listed below, will be performed per the methodology stipulated in each of the respective sections provided:

- Clinically relevant changes from baseline in vital signs (for more details, please see Section 3.7);
- Clinically relevant changes from screening in 12-lead ECG (for more details, please see Section 3.7);
- Clinically relevant changes from baseline in physical examinations (for more details, please see Section 3.7);
- Clinically relevant changes from baseline in safety laboratory assessments (hematology with differential count, biochemistry, and urinalysis) (for more details, please see Section 3.8);
- Plasma retinol and retinol-binding protein values, changes from screening/baseline, correlated with ophthalmological symptoms, specifically symptoms of nyctalopia. More precisely, Spearman correlation between plasma retinol and retinol-binding protein concentrations (change-from-baseline to Week 24) and the cumulative number of AEs for “nyctalopia” will be presented in scatter plot figures along with the regression line. Nyctalopia will be identified according to AEs of the following SOC/PT/LLT: Eye disorders/ Night blindness/ Nyctalopia.
- Change in PEx incidence and antibiotic treatment requirement (for more details, please see Section 3.14).

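### The SAP delivers the retinol/RBP correlation with eye assessments only through adverse events on one coded path, and never says how questionnaire symptoms reach that path

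*SAP*

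**What the plan says.** **The endpoint.** Protocol 7.1.4 lists "Correlation of plasma retinol and retinol-binding protein levels measured during the study with ophthalmological assessments", and SAP 2.8.1.3 repeats it. Protocol 11.5 explains that these assessments comprise both specific tests and a patient questionnaire. Protocol 12.5 restates the safety analysis as "Plasma retinol and retinol-binding protein values, changes from screening/baseline, correlated with ophthalmological symptoms, more specifically nyctalopia".

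**The implementation.** SAP 3.18 describes the target as values "correlated with ophthalmological symptoms, specifically symptoms of nyctalopia". It then specifies a Spearman correlation between the change from baseline to Week 24 in retinol or RBP and the cumulative number of nyctalopia AEs, shown as scatter plots. The case definition is "Nyctalopia will be identified according to AEs of the following SOC/PT/LLT: Eye disorders/ Night blindness/ Nyctalopia". SAP 3.11 (retinol and RBP) and SAP 3.16 (exploratory endpoints) contain no other correlation. The list of methodological changes in SAP section 5 does not mention this narrowing.

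**The questionnaire.** The NVQ covers "Question 1: Dark adaptation difficulties; Question 2: Vision in condition of poor luminosity; Question 3: Recovery after dazzling" (Protocol 11.5). One abnormal answer is handled as follows: "Level 1 NVQ will result in the given symptom to be considered a Grade 1 AE". For two or three, "Level 2 or 3 NVQ will automatically trigger a complete ophthalmological examination (Step 2) and its AE severity graded by the ophthalmologist". Reports that the examination does not confirm take Grade 1 by default.

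**The concern.** The endpoint is worded in terms of assessments, but the analysis uses neither of the two assessments the protocol names. It uses an AE count, and who enters that count depends on how a site words an event and how a coder places it. The plan fixes neither step.

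What is at stake is one exploratory safety result, though a relevant one. Protocol 5.4.3.1 gives lowered retinol as the likely route to the drug's expected eye effect, which it calls "reversible delayed dark adaptation (nyctalopia, also called night blindness". Protocol 11.2 allows retinol and RBP measurements to support decisions on treatment-emergent eye events. If events are lost to naming and coding, the plotted association will look weaker than it is, and the reader cannot tell by how much.

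**Working it through.** The plan states no figure on this point, so there is none to reproduce. The check has three steps.

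**1. Trace an NVQ report to the count (text only).**

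| Report | What the protocol fixes | AE term fixed? |
|---|---|---|
| Level 1 (one abnormal answer) | The symptom is a Grade 1 AE | No |
| Level 2 or 3 | Full eye examination; ophthalmologist grades severity | No |
| Level 2 or 3, not confirmed | Default Grade 1 | No |

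Protocol 11.1.2 prefers a clinical diagnosis to a bare abnormal result where possible, which favours recording nyctalopia. Protocol 11.5 separates reported symptoms from confirmed nyctalopia, which could lead a site to reserve that word for confirmed cases. Both practices are compatible with the text. SAP 3.18 gives a SOC/PT/LLT path without saying which level decides a match.

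**2. How wide the uncertainty is.** The documents give no split by NVQ Level, so every rate here is an assumption. Suppose each item is abnormal with probability *p*, from 0.05 to 0.30. With independent items, the share of NVQ-positive reports that are Level 1 is

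3p(1-p)² / [1-(1-p)³].

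- p = 0.05: 0.1354 / 0.1426 = 0.95
- p = 0.30: 0.441 / 0.657 = 0.67

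Correlated items were simulated with a latent-normal model over the same range of *p*. If every Level 1 report is missed and every Level 2-3 report is captured, the share missed is:

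| Latent correlation | Share missed |
|---|---|
| 0 | 67-95% |
| 0.6 | 45-72% |
| 0.9 | 26-43% |

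If only isolated dazzle-recovery reports are missed, the share is 9-32% across latent correlations from 0 to 0.9. With independent items it is one third of the Level 1 share, for example 0.95/3 = 0.32.

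**3. What random loss does to the correlation.** Assumed inputs: 136 patients, 68 per arm; retinol change with mean -1.2 on active and 0 on placebo, SD 0.6; Poisson AE counts with log-rate -2.0 - 0.9 × change. Each event is then kept with probability *q*. Results over 4,000 simulated trials:

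| q | Mean Spearman | Patients with an event | Trials with p < 0.05 |
|---|---|---|---|
| 1.0 | -0.35 | about 33 | 99% |
| 0.7 | -0.30 | about 25 | 95% |
| 0.5 | -0.26 | about 19 | 87% |
| 0.3 | -0.20 | about 12 | 69% |

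The trial-to-trial SD of the correlation is about 0.08. A second simulation (n = 120, different assumed event rates) shows the same pattern. With a mean of 0.5 events per patient, losing 25%, 50% or 75% moves about -0.43 to -0.38, -0.33 or -0.24. With a mean of 0.2, about -0.29 moves to -0.26, -0.22 or -0.16.

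**The case against.** A reader might infer that most questionnaire-detected events drop out, because each NVQ symptom is recorded under its own name and only the exact term Nyctalopia counts. The documents do not support that, for three reasons.

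- Protocol 11.5 makes a Level 1 symptom an AE but sets no term for it, and it sets none for Levels 2-3.
- The protocol's own vocabulary treats delayed dark adaptation as nyctalopia (5.4.3.1) and defines nyctalopia as poor vision at night or in poor light (8.2). Those descriptions are close to NVQ Questions 1 and 2, so sites have reason to use the word. Only dazzle recovery clearly falls outside, and leaving it out of a nyctalopia count is reasonable.
- The SOC/PT/LLT string can be read as matching at PT level. Strict LLT matching is an assumption.

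The consequence is also limited. SAP 3.10 tabulates NVQ answers and levels, all reported symptoms of nyctalopia and hemeralopia, and confirmed symptoms separately. SAP 3.18 tabulates all TEAEs. In step 3, 70% capture shifts the correlation by less than one trial-to-trial SD.

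Finally, the AE count has a merit of its own: it takes in the six telephone contacts that ask about vision (Protocol 9.2.4) and spontaneous reports. The NVQ misses these, so replacing the count by the NVQ would lose information.

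All of this stands against the stronger reading. It does not fill the gap: the endpoint as worded is not implemented, and inclusion in the count rests on an unwritten naming and coding practice.

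**Conclusion.** The point holds as a cheap improvement to an exploratory safety analysis. SAP 3.18 narrows a correlation with ophthalmological assessments to a count on one MedDRA path, uses neither the NVQ nor the examination, and leaves both the mapping and the matching level open.

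The share of reports left out is unknown. Under the assumptions tried it runs from 9% to 95%, so neither a large nor a small loss can be claimed. The direction, attenuation toward zero, depends on the loss being random with respect to retinol change. The sizes in step 3 depend on assumed event rates and an assumed true association. A reader might also conclude that the analysis would show retinol to be uninformative. That goes too far: even at 30% capture, about two thirds of simulated trials remain nominally significant, and the documents do not assign this correlation the role of deciding whether retinol can monitor eye toxicity.

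**What to change.** Amend SAP 3.18 before unblinding:

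1. Keep the AE-count correlation. State that matching is at PT Night blindness, and list any further terms that count, so that AEs arising from NVQ Questions 1 and 2 are included.
2. Add a Spearman correlation of retinol and RBP change with the worst post-baseline NVQ Level, or with a new abnormality on Question 1 or 2 compared with screening. NVQ and retinol/RBP are both already collected at screening and on Days 21, 77, 161 and 189.
3. Record the narrowing and the added analysis in SAP section 5.

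The cost is SAP wording and one extra exploratory output, with no new data. The drawback is that NVQ answers are subjective, and the protocol reports that symptoms in Phase Ib were not confirmed objectively. False positives attenuate too: in the step 3 simulation, adding an assumed 10% false-positive rate to fully captured counts also gives about -0.30. The two correlations should therefore be presented side by side.

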3.19 Interim Analysis

The following specific times have been selected a priori for DMSB meetings:

- When a minimum of half of the enrolled patients have completed at least one dosing cycle and corresponding safety information is available, along with Day 21 plasma retinol and retinol binding protein concentration data. This will not be a full unblinding; it will be an unblinded safety analysis of Active versus Placebo;
- When a minimum of half of the enrolled patients have completed the first 3 dosing cycles and corresponding safety data is available for review. This will not be a full unblinding; it will be an unblinded safety analysis of Active versus Placebo;
- Outside of the above, every 6 months;
- Anytime as needed for review of clinically significant safety information brought to the attention of the DSMB.

For more information, please see the DMC Charter as well as the DSMB Mock Tables document.

5 METHODOLOGICAL CHANGES FROM PROTOCOL

SAP Version (date)	Relevant Section in Protocol (Amendment 3 – dated: 31JUL2019)	Section (s) and Change (s) in SAP	Rationale for Change
Final v5.0 (dated: 08OCT2019)	Protocol Section 12.2 (Analysis Population); PEx Analysis Subset Population	SAP Section 3.3. (Analysis Population): 2 separate PEx Analysis Populations have been defined: 1) Protocol-Defined PEx Population (patients who experience a PEx with $\geq 4/12$ positive Fuch symptoms and treated with an IV antibiotic); 2) Overall PEx Population (patients who experience a PEx treated with an oral or IV antibiotic). This differs from the Protocol, wherein only one PEx Population, defined by patients treated with an IV antibiotic, is defined	To distinguish between PEx defined by Investigators based on clinical judgment and PEx defined by a standard criteria.
Final v5.0 (dated: 08OCT2019)	Protocol Section 12.2 (Analysis Population)	SAP Section 3.3. (Analysis Population): Addition of a definition of the Healthy Control Population used for the first secondary parameter.	To define the Healthy Control Population to be used in the assessment of pharmacodynamic parameters (AA, DHA and AA/DHA ratio)
Final v5.0 (dated: 08OCT2019)	Protocol Section 6 (Study Objectives-Secondary Objectives); Protocol Section 7.1.3 (Secondary Endpoints)	SAP Section 3.15 (Analysis of Secondary Endpoints): assessment of Overall PEx has been added, in addition to the assessment of Protocol-Defined PEx	To distinguish between PEx defined by Investigators based on clinical judgment and PEx defined by a standard criteria.
Final v5.0 (dated: 08OCT2019)	Protocol Section 12.5.1 (Adverse Events), 12.5.2 (Clinical Laboratory Assessments)	SAP Section 3.18 (Analysis of the Safety Endpoints): removal of the methodology related to the Fisher's Exact test to assess between-group differences in treatment emergent and clinically significant AEs	This phase 2 trial was not designed to test specified hypotheses about safety. Therefore, the Fisher's exact test will not be performed. AEs will be presented descriptively, and a qualitative evaluation will be performed.
Final v6.0 (dated: 03SEP2021)		SAP Section 3.14 (Analysis of the primary efficacy endpoints): Success of the study will be based on the primary efficacy endpoint assessment in the ITT Population. The PP population, Protocol-defined PEx Population and Overall PEx Population will serve for confirmatory analyses	To clarify that the success of the study will be based on the primary analysis, not the primary and all the secondary analyses.

RESPONSIVE
RELIABLE
RESULTS

APPLAUD (LAUCAN104201)
Statistical Analysis Plan
Version 6.0
September 03, 2021
Page 41 of 237

Final v6.0 (dated: 03SEP2021)	Protocol Section 12.4.1 (Analysis of primary endpoint)	SAP Section 3.14 (Analysis of the primary efficacy endpoints): the analysis of the primary efficacy endpoint will be repeated with the addition of the following covariates in the model: baseline use of Trikafta (yes versus no) and for the effect of the pandemic confinement (pre versus post pandemic onset)	To assess the impact on study results of the concomitant use of Trikafta and COVID-19 pandemic which occurred during the course of the trial.
Final v6.0 (dated: 03SEP2021)	Protocol Section 12.2 (Analysis Population)	SAP Section 3.14.1 (Subgroup Analyses): addition of subgroup analyses for baseline use of Trikafta (yes versus no) and for the effect of the pandemic confinement (pre versus post pandemic onset)	To assess the impact on study results of the concomitant use of Trikafta and COVID-19 pandemic which occurred during the course of the trial.

